Appendix 3. Variable Availability by Country (final list to be confirmed in SAP)

LEGEND: "--" indicates that the information is not available

Partial = may be available for some patients

Limited = anticipated to be underreported

Yes = likely to be available if true for patient

Unlikely = available for some patients; may not be accurate

Calculated = assumptions can be used to derive a variable for this information

Variable	US	Denmark	Norway	Sweden	Finland
Mysimba prescription	Yes				
Date of Mysimba	Yes				
prescription					
Mysimba dispensing	Partial	Yes	Yes	Yes	Yes
Date of Mysimba	Partial	Yes	Yes	Yes	Yes
dispensing					
Mysimba dosage for each	Partial				
dispensing					
Initial titration scheme	Maybe				
Dosing of Mysimba during	Maybe				
titration					
Dose adjustment of	Partial				
Mysimba (e.g., for special					
population)					
Maintenance dose of	Maybe				
Mysimba					
Mysimba days' supply	Calculated	Calculated	Calculated	Calculated	Calculated
Date of	Partial	Yes	Yes	Yes	Yes
eligibility/enrolment					
available to identify					
continued					
engagement/recording of					
clinic visits					
Age	Yes	Yes	Yes	Yes	Yes
Sex	Yes	Yes	Yes	Yes	Yes
BMI	Partial				
Height	Partial				
Weight	Partial				
Diabetes	Yes	Yes	Yes	Yes	Yes
Dyslipidaemia	Yes	Yes	Yes	Yes	Yes

Proprietary and Confidential:

This document cannot be used, distributed, or reproduced in any way without the prior written consent of Currax Pharmaceuticals LLC.

Anorexia nervosa	Yes	Yes	Yes	Yes	Yes
Bulimia	Yes	Yes	Yes	Yes	Yes
Hypertension	Yes	Yes	Yes	Yes	Yes
Uncontrolled hypertension	Yes	Yes	Yes	Yes	Yes
Moderate or severe renal	Yes	Yes	Yes	Yes	Yes
impairment	1 68	1 68	1 68	1 68	1 68
End-stage renal disease	Yes	Yes	Yes	Yes	Yes
Seizure	Yes	Yes	Yes	Yes	Yes
Seizure disorder	Maybe	Unlikely	Unlikely	Unlikely	Unlikely
Hepatic impairment via	Maybe				
Child-Pugh score	Mayoc				
Hepatic impairment via diagnosis	Yes	Yes	Yes	Yes	Yes
Central nervous system	Yes	Yes	Yes	Yes	Yes
tumour					
Substance use/abuse	Limited	Limited	Limited	Limited	Limited
Acute opiate withdrawal	Limited				
Acute alcohol or	Limited				
benzodiazepine withdrawal					
Suicidality	Limited	Limited	Limited	Limited	Limited
Mania	Limited	Limited	Limited	Limited	Limited
Bipolar disorder	Limited	Limited	Limited	Limited	Limited
Major depressive disorder	Yes	Yes	Yes	Yes	Yes
Hepatotoxicity	Yes	Yes	Yes	Yes	Yes
Severe hypersensitivity reaction	Limited	Limited	Limited	Limited	Limited
Cardiovascular-related	Partial	Partial	Partial	Partial	Partial
death	1 artiar	1 artiar	1 artiai	1 artiar	1 artiar
Non-fatal myocardial	Yes	Yes	Yes	Yes	Yes
infarction					
Non-fatal stroke	Yes	Yes	Yes	Yes	Yes
Use of naltrexone (other	Yes	Yes	Yes	Yes	Yes
than Mysimba)	Vaa	Vaa	Vac	Vac	Vaa
Use of bupropion (other than Mysimba)	Yes	Yes	Yes	Yes	Yes
, , , , , , , , , , , , , , , , , , , ,	Vac	Vac	Vac	Vac	Yes
Use of CYP2B6 inhibitor	Yes	Yes	Yes	Yes	
Use of CYP2B6 inducer	Yes	Yes	Yes	Yes	Yes
Use of CYP2B6 substrate	Yes	Yes	Yes	Yes	Yes
Use of CYP2Db substrate	Yes	Yes	Yes	Yes	Yes
Use of medicine that lowers	Yes	Yes	Yes	Yes	Yes
seizure threshold	Vac	V	V.	V	Var
Opioid or opiate agonist	Yes	Yes	Yes	Yes	Yes
prescription or dispensing					

MAOI prescription or	Yes	Yes	Yes	Yes	Yes
dispensing	1 05	1 05	1 05	1 05	105
Pregnancy	Yes	Limited	Limited	Limited	Limited
Breastfeeding	Limited	Limited	Limited	Limited	Limited
Death	Partial	Yes	Yes	Yes	Yes
Disenrollment	Partial	Partial	Partial	Partial	Partial
Socioeconomic data		Partial	Partial	Partial	Partial
Laboratory results	Limited	Limited	Limited	Yes	Limited
Surgical procedures	Yes	Yes	Yes	Yes	Yes
Diagnostic testing results	Limited	Limited	Limited	Yes	Limited
Indication (reason) for	Partial				
treatment with Mysimba					
Discontinuation and date of	Calculated	Calculated	Calculated	Calculated	Calculated
discontinuation of					
Mysimba					
Reason(s) for treatment	Partial-no				
discontinuation	attribution				
Discontinuation due to	Partial-no				
adverse event	attribution

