6. MILESTONES

Milestone	Nordic Registries Study	U.S. Study	
	Anticipated Dates	Anticipated Dates	
Study protocol resubmitted to EMA	November 21, 2022	November 21, 2022	
Protocol approved by EMA	December 15, 2022*	December 15, 2022*	
Registration in EU PAS Register	January 15, 2023	January 15, 2023	
Apply for registry data for secondary	September 15, 2023 (post	N/A	
use	EC approval)		
Data receipt and start date for data	December 29, 2023	February 15, 2023	
analysis			
Interim report of study results #1**	April 15, 2024	N/A	
Interim report of study results #2***	April 15, 2025	N/A	
Final report of study results****	December 31, 2025**	August 4, 2023**	

^{*} Subsequent dates are dependent on timing of protocol approval by EMA

^{**} Based on counts of patients prescribed/dispensed Mysimba/Contrave through the end of 2021 and assuming both 80% are captured in the databases and 80% of identified patients are new users with at least 365 days continuous eligibility in data source before first Mysimba/Contrave prescription/dispensing, then there should be >3,000 eligible patients in data sources from US, Norway, Finland and possibly Sweden in this

analysis; it is uncertain at this time whether there will be at least 750 patients in Denmark during the conduct of the NB-451 study. Data for this interim study report will be the data available by December 29, 2023; it is likely that data will only be available through 2021 at this time.

*** A second interim report will only be included if Denmark identifies 750-3,000 eligible patients who would be available before December 31, 2024.

**** Final report date dependent on accumulation of data from the four Nordic country databases. Based on counts to date and projections of new users, there should be >3,000 eligible patients in the Norway and Finland data sources at the end of 2023. The 2023 data from Norway and Finland are expected to be available in late 2024. If final data are available in late 2024, the December 2025 final report will include the new final results from Norway, Finland, and Sweden, with updated interim or final analyses in Denmark, if appropriate.. Additionally, the final report will provide synthesis across all four Nordic data sources.

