9.1.1. Inclusion Criteria

Patients will be included in the study if they meet the following inclusion criteria:

- 1. At least one prescription of Mysimba/Contrave in his/her medical records any time during the study period (US) OR at least one dispensing of Mysimba/Contrave in his/her registry any time during the study period (Nordic);
- 2. At least 365 days of computerized records prior to first Mysimba/Contrave prescription or dispensing date; and 3Patient is active (i.e., alive and registered/accruing data) at the time of the first Mysimba/Contrave prescription or dispensing date.

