9.3. Variables

9.3.1. Exposure

Exposure to Mysimba/Contrave will be identified through medication prescription or dispensing data (i.e., prescription or dispensing date, dosage [where available], and duration [where available]). The first Mysimba/Contrave prescription after 365 days with no prescription will be the index date, as depicted in Figure 1. All prescriptions of Mysimba/Contrave (or the two component products dispensed within 15 days) during the 548 days (18 months) following the index date will be captured. Patients will be assessed during the entire 548 days following the index date.

Figure 1. Index date, Exclusion and Covariate Assessment, and Follow-up Time for Study

Index Date (First prescription of Mysimba) Day 0

- a. Data are 'acceptable for research' for the patient and practice, coverage with computerized records throughout time period with no gaps
- b. Baseline conditions included: BMI, height, most recent weight, weight-related comorbidities (e.g., diabetes, dyslipidaemia), neuropsychiatric conditions (mania, bipolar disorder, major depressive disorder [MDD], anorexia nervosa, bulimia), hypertension, end-stage renal disease, seizure disorder, hepatic impairment (defined by Child-Pugh score category), central nervous system tumour, substance use/abuse including acute opiate withdrawal,;uncontrolled hypertension, seizures, bipolar disorder, MDD, anorexia nervosa, or bulimia; use of: naltrexone, bupropion, opioid or opiate agonist, or MAOI; pregnancy, or breastfeeding
- c. Earliest of: death, disenrollment, 548 days of follow-up, end of the study period

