9.3.3. Covariates

When available, the following variables needed to conduct analysis for the primary and secondary research objectives will be collected. Variable availability from each country will be summarized in the SAP and is included in Appendix 3 in draft form.

Demographics and Baseline variables (Within 365 days before index date unless otherwise stated below; as depicted in Figure 1):

- 9. Patient demographics (age and sex on index date) (obtained directly from data source)
- 10. BMI, height, weight (most recent value on or before the index date) (obtained directly from data sources; BMI may be calculated if height and weight available)
- 11. Relevant comorbidities (obtained via ICD-10 codes), including:
 - 1. Weight-related comorbidities (i.e, type 2 diabetes, dyslipidaemia, hypertension)
 - 2. Neuropsychiatric conditions (mania, bipolar disorder, major depressive disorder [MDD], anorexia nervosa, bulimia)
 - 3. Uncontrolled hypertension, if possible
 - 4. Moderate or severe renal impairment
 - 5. End-stage renal disease
 - 6. Seizure disorder
 - 7. Hepatic impairment (defined by Child-Pugh score category, if available)
 - 8. Central nervous system tumour

- 12. History of, or current substance abuse/dependencies including acute opiate withdrawal (obtained via ICD-10 codes)
- 13. History of uncontrolled hypertension, seizures, bipolar disorder, MDD, anorexia nervosa, or bulimia (obtained via ICD-10 codes)
- 14. Prior medication use, including: naltrexone, bupropion, CYP2B6 inhibitors, CYP2B6 inducers, CYP2B6 substrates, CYP2D6 substrates, Monoamine oxidase inhibitors, Opioids, Opium alkaloids and derivatives and drugs that lower seizure threshold (obtained via ATC [Nordic data] or NDC [US data]) see Appendix 2 and 2A
- 15. Pregnancy status and breastfeeding status (obtained via ICD-10 codes)

All variables will be identified from the data sources outlined below using a pre-specified list of definitions per database (Appendix 3), to be defined in the SAP as final.

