9.4.2. United States Data Source

An EHR or claims-based integrated database across multiple healthcare systems in the United States, providing a representative mix of US Commercial Insurance and Medicare (major systems of health insurance in the US) has been selected. Arcadia Data Research was chosen as the US data for this study because of their approximately ten-year history of successfully curating data for health systems that are substantially involved in value-based care, which necessitates high-quality clinical data across the included patient populations. Data incorporated into the US dataset will include electronic medical records from multiple systems, laboratory test orders, and prescription data. Moreover, a sizeable proportion of the EHR population will also have their health insurance claims records linked in their final (adjudicated) form. The typical data extract will include (but is not limited to): patient demographics and characteristics (including height and weight or BMI if available), medical encounters, appointments, provider data, charges, assessments, immunizations, health maintenance and medical history, laboratory orders/results, vital signs (e.g., blood pressure, heart rate), patient insurance, prescriptions and active medications, problem lists, and patient allergy information. EHR data are sourced from large integrated delivery networks, academic medical centres, ambulatory care, primary care, core hospitals, and others. The data are coded in standard vocabularies used within the US, including ICD-10, NDC, CPT, LOINC, etc. Additional information, such as social determinants of health will be captured, if available. The data are expected to contain sufficient information to elucidate occurrence and determine levels of all variables, with the following exceptions which may be prone to misclassification due to limited coding in administrative and clinical data: neuropsychiatric conditions, history or current substance use or dependence, breastfeeding status, and reason(s) for medication discontinuation.

The integration of claims data for a subset of patients will be important for this study in order to capture pharmacy prescriptions dispensed and for better capture of MACE events. The selected database will be described in more detail in the US SAP.

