We anticipate that the US dataset will include >20,000 new users of Contrave who will be eligible for inclusion in the study as of December 31, 2022. The final analysis of the US database will be conducted and presented in a US only study report.

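### Inclusion criterion 2 omits the no-gap baseline coverage that Figure 1 requires, and enrolment dates cannot verify that coverage for some US patients

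*Protocol*

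**What the plan says.** Section 9.1.1, like the synopsis, sets the baseline criterion as "At least 365 days of computerized records prior to first Mysimba/Contrave prescription or dispensing date". Its third criterion asks that the patient be alive and accruing data, but only at the index date. Section 9.1.2 applies no exclusions.

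Two other places ask for more. Figure 1 note a in section 9.3.1 describes the period as having "coverage with computerized records throughout time period with no gaps". The footnote to the milestones in section 6, which covers the US as well as Nordic sources, assumes that "80% of identified patients are new users with at least 365 days continuous eligibility in data source".

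Appendix 3 rates, by country, the date of eligibility or enrolment that would identify continued engagement. The row reads "Date of Partial Yes Yes Yes Yes", in the order US, Denmark, Norway, Sweden, Finland. The legend says "Partial = may be available for some patients". Section 9.4.2 describes the US source as EHR data from several systems, in which "a sizeable proportion of the EHR population will also have their health insurance claims records linked"; the share is not given. It also states: "We anticipate that the US dataset will include >20,000 new users of Contrave".

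Baseline variables are taken "Within 365 days before index date unless otherwise stated below" (section 9.3.3), mostly from codes. Section 8 defines AESIs as new onset and makes the number and percentage of compliant and non-compliant patients a primary objective.

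**The concern.** The operative criterion is looser than the condition stated elsewhere in the same protocol. A registry covering residents until death or emigration makes the difference immaterial, but a multi-system EHR does not. There, a patient can have a first record more than 365 days before index and no observed care in the year before it, and still meet section 9.1.1.

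Such a patient may carry no codes for contraindications, comorbidities or prior drug use in the baseline window. If no code is read as no condition, the patient can be classified as free of contraindications, and a long-standing condition first coded after index can enter as a new-onset AESI. The new-user definition has the same weakness, since it rests on 365 days without a prescription (section 9.3.1). The US is expected to be a large cohort, and Nordic enrolment dates are rated Yes throughout. A US-Nordic difference could therefore partly reflect how well baseline was observed.

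**Working it through.** The protocol states no figure on this point, so there is none to reproduce. The check sets the sections side by side, followed by an illustration on assumed inputs.

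**Step 1: the condition.**
- Section 9.1.1: 365 days of records, with no mention of continuity.
- Figure 1 note a: coverage without gaps.
- Section 6: continuous eligibility, assumed in the counts.

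The sponsor intends continuity, but the criterion that admits patients does not carry it.

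**Step 2: can it be verified?** Appendix 3 rates the enrolment date Yes in four Nordic countries and Partial in the US. Section 9.4.2 links claims for a subset only. So for some US patients enrolment dates cannot show the no-gap condition. No section restricts the US cohort to patients with dates or gives another test.

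**Step 3: what happens to an unobserved baseline?** Section 9.7.5 reports and imputes missing values, including comorbidities and history, but does not say when the absence of a code counts as missing. Section 9.9.1 warns in general that diagnoses without a medical encounter may not be captured. It does not connect this with baseline classification or US enrolment.

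**Step 4: scale, on assumed inputs.** Let N = 20,000 (the lower bound in section 9.4.2), f = share of US patients with an unobserved baseline, p = true prevalence of a contraindication, r = prevalence of a pre-existing AESI condition, q = probability that it is coded during follow-up. The documents give none of f, p, r or q.

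Contraindicated patients not seen = N × f × p; observed prevalence = p × (1 − f):

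| f | p | Not seen | Observed prevalence |
|---|---|---|---|
| 0.10 | 0.02 | 40 | 1.8% |
| 0.10 | 0.10 | 200 | 9% |
| 0.30 | 0.10 | 600 | 7% |
| 0.50 | 0.10 | 1,000 | 5% |

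Spurious new-onset events per 1,000 persons = 1,000 × f × r × q:
- lowest: 1,000 × 0.10 × 0.01 × 0.25 = 0.25
- highest: 1,000 × 0.50 × 0.10 × 0.75 = 37.5

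The results span a factor of 25 (1,000/40) and of 150 (37.5/0.25), so they show how the error works and do not estimate it.

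**Step 5: direction for the overall non-compliance percentage.** Section 9.7.2 also counts as non-compliant a patient without evidence of obesity, or of overweight with a weight-related comorbidity. Appendix 3 rates US BMI Partial, and section 9.3.2 falls back on codes when BMI is unavailable. Among unobserved patients, let c be the share who are non-compliant only through a contraindication that is not seen, and m the share who are compliant but lose the evidence of their indication. The net change is f × (m − c). Its sign depends on m and c, and the documents give neither.

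**The case against.** The strongest reply is that the no-gap condition is already in Figure 1, that Appendix 3 is a draft to be confirmed in the SAP, and that section 9.4.2 leaves further description of the US database to a US SAP. An observability rule for one EHR source could properly be there. In addition, the US extract includes encounters, appointments, problem lists, medical history and active medications. Activity can therefore be derived without enrolment dates, and a patient without a baseline-year encounter need not be blank at index. Sections 9.4.2 and 9.9.1 already concede some misclassification and incomplete capture.

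Much of this stands and limits the point. Three stronger readings are tempting but unsupported:
- A reader might infer that the US baseline is accepted on elapsed records alone. Figure 1 note a says otherwise.
- A reader might equate the patients without enrolment dates with those lacking linked claims. No section makes that link.
- A reader might conclude that US non-compliance is biased down, or that a given share of new-onset events is false. Step 5 shows the sign is open, and every input to such a share other than the cohort size would be assumed.

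The reply does not remove the mismatch between section 9.1.1 and Figure 1. Inclusion criteria are protocol content, and a database description in the SAP would not by itself reconcile them.

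**Conclusion.** The point holds as an internal inconsistency with a practical consequence. Section 9.1.1 omits a condition that Figure 1 states and section 6 assumes, and Appendix 3 shows that enrolment dates cannot verify it for part of the US cohort.

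If absence of a code is scored as absence of the condition, individual contraindications and prior use may be under-counted, and pre-existing conditions may be counted as new-onset AESIs. That scoring rule is the natural reading of code-based definitions, but the protocol does not state it. The net effect on the primary non-compliance percentage may go either way. The documents do not allow the size of any of these effects to be estimated.

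The change is worth making because it is cheap and because stratified tables would show whether the problem matters.

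**What to change.** Carry the no-gap condition into section 9.1.1 and state how the US data meet it:
- Where enrolment dates exist, require continuous enrolment from day −365 to day −1.
- Otherwise, require a first record at least 365 days before index and at least one recorded encounter in the baseline year before the index visit. Describe this as a minimum activity rule. One encounter does not prove gap-free observation and will not reveal Contrave use in another health system.

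Report the US compliance and AESI tables separately for patients with verified continuous enrolment and for the rest.

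The cost is protocol wording and one extra set of US tables. Section 6 anticipated the US final report on August 4, 2023, before the August 7, 2023 date given for the last protocol version. If that report is already done, the tables would be a supplementary analysis. Some patients known only from EHR data would be lost, with a slight shift towards more frequent users of care. Precision is unlikely to suffer: the target of about 3,000 per database (section 9.5) is 3,000/20,000 = 15% of the expected US cohort.

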- 6. Serotonin syndrome
- 7. Major adverse cardiovascular events (i.e., cardiovascular-related death, non-fatal myocardial infarction, or non-fatal stroke)

Deaths will also be described by treatment group, for those with vital status available.

- 7. Treatment discontinuation (assessed using ATC [outpatient, Nordic data] or NDC [US data])
- 8. Reason(s) for treatment discontinuation (obtained via ICD-10 codes in the 90 days prior to discontinuation)

All variables will be identified from the data sources via a pre-specified list of definitions (i.e., code lists; see Appendix 2). Occurrence of AESI based on diagnostic codes will be summarized for all patients, and for a subgroup of patients who do not adhere to conditions of the EU SmPC for the Scandinavian countries (adapted to local SmPC as needed) or to the FDA SmPC for the US. Such criteria include: not meeting appropriate criteria for the indication [obese (BMI \geq 30 kg/m²), or being overweight (BMI \geq 27 kg/m² to < 30 kg/m²) and having at least one weight-related co-morbidity (e.g., type 2 diabetes, controlled hypertension, or dyslipidemia) based on diagnostic codes. If BMI is not available, diagnostic and procedure codes for obesity and weight loss will be applied, recognizing that it will likely produce a more obese population than would be identified by BMI. Subgroup analyses will also be conducted to assess continuous treatment in patients with either renal or hepatic impairment.

Initiation of specific medications that could result with the occurrence of an event corresponding to an AESI (e.g., newly initiating anti-epileptic/seizure medication, newly initiating medications indicated for mania or depression) will also be tabulated. For hepatotoxicity, liver function tests can be used (when available) in addition to diagnostic codes.

For reason(s) patients who discontinue treatment (i.e., do not refill their prescription), events (potential AESIs and contraindications) and clinical status (magnitude of weight loss or gain)

Proprietary and Confidential:

occurring within the 90-day window prior to discontinuation will be summarized. It should be noted that weight may not be available in the Scandinavian registries.

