All citizens of these countries are represented in these national registries until death or emigration, providing virtually complete long-term follow-up. Identification of individuals by their unique personal identifier permits linkage to other national health databases (Laugersen et al., 2021). Thus, a large amount of specialized information from specific registries, such as hospitalization, prescription, heart disease, and death registries, can be linked for research (Schmidt 2015; Laugersen et al., 2021). The registries are highly complete and accurate due to the automation of their processes, as well as laws and other incentives motivating healthcare providers to collect and send the data electronically to their national databases (Gribsholt et al., 2019). The data from each country are expected to contain sufficient information to elucidate occurrence and determine levels of all variables, with the following exceptions which may be prone to misclassification due to limited coding in administrative and clinical data: obese or overweight with at least one comorbidity, neuropsychiatric conditions, history or current substance use or dependence, breastfeeding status, initial titration scheme and dose adjustments (expected to be unavailable since only one dose/pack type is available in the Nordic countries and no measure of titration scheme or adherence is included within the data), and reason(s) for medication discontinuation. Any country database with at least 750 patients with at least 365

days of data before the index Mysimba use and at least 548 days of availability in the data after the index date of Mysimba will be evaluated for whether there is sufficient required patient data to conduct this study. If there is sufficient data and uptake indicating that the database will reach more than 3,000 patients within the timespan of this drug utilisation and safety study, then it will be added to the data sources for evaluation. It should be noted that reimbursement varies in Scandinavia, with no reimbursement for Mysimba in Sweden and Denmark, and reimbursement in Norway and Finland restricted to morbidly obese patients who are at higher risk of cardiovascular and other events.

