9.7.2. Descriptive Statistics

For demographic and baseline variables and duration of Mysimba/Contrave use (measured as both continuous treatment of the initial Mysimba/Contrave duration and the total treatment duration of Mysimba/Contrave), descriptive statistics will be used to describe continuous variables, (e.g., mean, standard deviation, median, quartiles 1 and 3, minimum, maximum, and two-sided 95% confidence intervals [CI]). Categorical variables will be described by the total and percentage of each response and the number of missing data (data that are unavailable in the database).

Patterns of Mysimba/Contrave use will be described by mean (standard deviation, SD) and median (quartile1, quartile 3) number of prescriptions per patient, number and duration of treatment episodes per patient as well as the average duration between prescription episodes. Analyses will be performed for all users of Mysimba/Contrave, including an assessment of whether the subjects have adhered to the prescribed treatment with Mysimba/Contrave according to the terms of the SmPC (adapted to the local country SmPC for the data source as needed, and adapted if BMI is not accessible). The number and proportion of patients who received treatment with Mysimba/Contrave will be provided according to the following subgroups (availability of variables to be summarized in SAP):

(a) Inconsistent with labelled indication:

- 1) Age < 18 years
- 2) Use other than management of weight
- 3) Management of weight in a patient who does not have obesity or is not overweight and has a weight-related comorbidity
- 4) A prescribed maintenance dose other than the Mysimba/Contrave 32mg/360mg
- 5) Continued use past 16 weeks without \geq 5% weight loss
 - (b) Incompatible with the stated contraindications set out in the SmPC:
- 1) A current diagnosis of uncontrolled hypertension, seizure disorder (or history of seizures), or end-stage renal failure
- 2) A history bipolar disorder, anorexia nervosa or bulimia
- 3) A current dependence on chronic opioids or opiate agonists (e.g., methadone)
- 4) A current state of acute opiate withdrawal
- 5) Any concomitant treatment containing bupropion, naltrexone, or a MAOI
- 6) Patients with a known central nervous system tumour
- 7) Patients undergoing acute alcohol or benzodiazepine withdrawal
- 8) Patients with severe hepatic impairment

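### Baseline seizure status rests on ICD-10 codes from one year, which Appendix 3 rates as possibly inaccurate in the Nordic sources, and baseline dispensing is never used to recognise prevalent disease

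*Protocol*

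**What the plan says.** **Baseline definition.** Section 9.3.3 sets the window: "Demographics and Baseline variables (Within 365 days before index date unless otherwise stated below". Within it, seizure disorder falls under "Relevant comorbidities (obtained via ICD-10 codes), including", and history is a separate item: "History of uncontrolled hypertension, seizures, bipolar disorder, MDD, anorexia nervosa, or bulimia (obtained via ICD-10 codes". No longer window is given for the history item. Prior medication is also collected, but as interaction classes, MAOIs, opioids and drugs that lower the seizure threshold. No dispensing is linked to a baseline condition.

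**Use of that status.** Section 9.7.2 lists as a contraindication: "A current diagnosis of uncontrolled hypertension, seizure disorder (or history of seizures), or end-stage renal failure". Section 8 makes SmPC compliance a primary objective, compares AESIs between compliant and non-compliant users, and defines AESIs as new onset.

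**Data quality.** Appendix 3 has "Seizure disorder Maybe Unlikely Unlikely Unlikely Unlikely", in the order US, Denmark, Norway, Sweden, Finland. The separate row for Seizure is Yes in all five sources. So is depression: "Major depressive disorder Yes Yes Yes Yes Yes". Yet 9.4.1 counts among the variables prone to misclassification "neuropsychiatric conditions, history or current substance use or dependence, breastfeeding status", and 9.4.2 makes the same reservation for the US. Appendix 2 gives one entry for seizures, G40, and none for seizure disorder or history of seizures.

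**Dispensing as a marker.** Sections 9.3.2 and 9.7.3 tabulate, after index, "newly initiating anti-epileptic/seizure medication, newly initiating medications indicated for mania or depression" as possible signs of an AESI. Section 9.4.1 describes the Nordic registries as having a strong record for measuring exposure to prescription drugs.

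**The concern.** The variable that settles the seizure contraindication is one the protocol itself doubts in all four Nordic sources. The better-measured source, dispensing, is accepted as a sign of seizure disease after index but not before it.

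A patient on antiepileptic treatment with no G40 code in the baseline year would be handled wrongly twice. First, the patient is scored free of the contraindication, so contraindicated use is understated. Second, the next G40 contact can be counted as a new-onset seizure, and in the compliant group. That raises seizure incidence among compliant users and narrows the contrast with non-compliant users. Few true seizures may occur per database, so a handful of such patients could matter.

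The second mechanism also applies to depression and mania. The first does not, because neither is itself a listed non-compliance criterion (bipolar disorder is, under its own code).

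**Working it through.** **1. Reading the definitions together.** The contraindication covers seizure disorder or a history of seizures. Both come from ICD-10 codes in 9.3.3, and Appendix 2 offers only G40. The same code therefore appears to serve the baseline variable and the outcome. Nothing in 9.3.3 or 9.7.2 adds a second source.

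**2. Removal of prevalent cases.** Section 9.7.3 divides the incidence proportion by all initiators. The rate uses an at-risk population that is not defined further. A wash-out on baseline codes would still leave uncoded prevalent patients in.

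**3. The protocol's own scale.** Section 9.5 states that no events in 3,000 patients bounds the risk at 0.1%. The exact bound is 1 − 0.05^(1/3000) = 0.0998%, so it reproduces. It gives scale only and is not a seizure rate.

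**4. Illustration for seizures.** The documents give neither prevalence nor code sensitivity, so these inputs are assumptions:
- true new-onset risk 0.1%;
- prevalent seizure disorder, prev, 0.2% to 1%;
- sensitivity of the baseline code, sens, 50% to 90%;
- chance that a missed prevalent patient is coded during the counting window, q, 10% to 50%.

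Per 3,000 users:
- missed = 3,000 × prev × (1 − sens)
- false events = missed × q
- true events = 3,000 × (1 − prev) × 0.001
- ratio = (true + false) / true

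| prev | sens | q | missed | false | true | ratio |
|---|---|---|---|---|---|---|
| 0.2% | 90% | 10% | 0.6 | 0.06 | 2.99 | 1.02 |
| 0.5% | 70% | 30% | 4.5 | 1.35 | 2.98 | 1.45 |
| 1% | 50% | 50% | 15 | 7.5 | 2.97 | 3.53 |

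**5. Illustration for depression.** Let d be the share treated, h the share of those with a baseline code, a the yearly rate of coded contact in uncoded prevalent users, and b the rate in unaffected users. The share of apparent new-onset depression that is really prevalent is d(1 − h)a / [d(1 − h)a + (1 − d)b]. Take b = 0.5% per year, and (d, h) from (15%, 30%) to (25%, 10%). With a = 3% the share is 0.43 to 0.64; with a = 1% it is 0.20 to 0.38. All four inputs are assumed, and the answer moves with a.

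**The case against.** Several points on the other side are sound.

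- **The Seizure row is Yes in every source, and history of seizures is part of the criterion.** Some patients missed under seizure disorder may be caught this way. But Appendix 2 supplies only G40, so the Yes and the Unlikely appear to rest on the same code. The two ratings conflict, and the better one cannot simply be relied on.
- **The SAP may settle it.** The protocol requires new onset, refers to an at-risk population, plans AESI-definition sensitivity analyses where data allow, and calls Appendix 3 a draft. The SAP may well set a wash-out rule. However, 9.3.3 already names ICD-10 codes as the source, and the planned sensitivity analyses concern the AESI, not baseline status or compliance.
- **Misclassification is disclosed.** True for neuropsychiatric conditions (9.4.1, 9.4.2) and for diagnoses made outside a medical encounter (9.9.1). Disclosure does not bound the effect.

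A reader might infer three stronger things that the documents do not support:

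- **That the protocol rates baseline depression codes as inaccurate.** Appendix 3 rates MDD Yes throughout; only the general caveat points the other way.
- **That missed depression lets a patient pass as compliant.** Depression is not a compliance criterion.
- **That antiepileptic and antidepressant dispensing is ignored before index.** Judging new initiation needs a look-back, and the CYP2B6 and CYP2D6 lists include citalopram, fluoxetine, carbamazepine and phenytoin. What is missing is their use to recognise baseline disease.

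**Conclusion.** The point holds for seizures. The baseline definition is code-only, its default window is one year, the protocol doubts it in the Nordic sources, and it decides a compliance criterion. That uncoded prevalent patients will be counted as new onset is a consequence the current text permits, not one it states. For depression and mania, only the new-onset count is exposed.

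The size is open. Under the assumed inputs, 0.6 to 15 patients per 3,000 would be scored free of the seizure contraindication in error, and the apparent seizure risk would be 1.02 to about 3.5 times the true one. The effect could be negligible or dominant. A reader might take from such figures that seizure incidence is roughly doubled, or that most new-onset depression is prevalent. The documents support neither: the 0.1% is a hypersensitivity example and a zero-event bound, and the depression share falls below one half once the assumed contact rate is lowered. The case for a change rests on the plan offering no way to tell which situation applies.

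**What to change.** 1. **Section 9.7.3:** add a pre-specified sensitivity analysis. Its at-risk set for new-onset seizure, depression and mania excludes patients with a baseline diagnosis or a baseline dispensing of, respectively, an antiepileptic, an antidepressant other than bupropion, or a mood stabiliser. Keep the diagnosis-only result alongside.
2. **Section 9.7.2:** report the seizure contraindication with and without the baseline antiepileptic marker. Present the two as a sensitivity range, not strict bounds, since patients neither coded nor treated are still missed.
3. **Appendix 3:** reconcile Seizure (Yes) with Seizure disorder (Unlikely), given the single code entry in Appendix 2. Reconcile MDD (Yes) with the caveat in 9.4.1 and 9.4.2. The documents give no ground for downgrading MDD in particular countries only.

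**Cost:** protocol and SAP wording, drug-class code lists and one more at-risk definition. The planned tabulation of newly initiated drugs already needs those classes and a look-back on them, so little or no new extraction should be required. The drawback is that these drugs have other indications, so the sensitivity analysis removes some users who are truly at risk. That is why it should sit beside the diagnosis-only result and not replace it.
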